13.1.2 Analysis of Secondary Endpoints

The objective response rate (partial response or better according to the modified IMWG criteria) and the proportion of patients with a MRD, CR, PR or MR will be reported with 90% exact binomial confidence interval (CI). The exact 90% CI around response rate will be no wider than 28% with 39 eligible patients.

Time to progression (TTP) is defined as the time from protocol therapy initiation until documented progression, censored at date last known progression-free for those who have not progressed.

To estimate the duration of response (time from objective response to disease progression or death, or date last known progression-free and alive for those who have not progressed or died), progression-free survival (time

CONFIDENTIAL

This document is confidential. Do not disclose or use except as authorized.

from protocol therapy initiation to the disease progression or death from any cause, censored at date last known progression free for those who have not progressed or died), and overall survival (time from protocol therapy initiation to death or date last known alive), the Kaplan-Meier method will be used.

It is expected that approximately 20% of the patients will receive cyclophosphamide (CTX) for mobilization and this may influence the PFS. Therefore, in a secondary analysis the 2 year PFS rate will be evaluated among those patients who did not receive CTX. Assuming that among the 39 eligible patients between 5-20% of the patients receive CTX for mobilization, the treatment will be considered promising if the observed response rate is at least 62%. With this rule, there is at least 80% probability of concluding the treatment is effective, when the true rate is 70% and less than 10% if true rate is 50%.

Safety analysis will be conducted using the Safety Population defined as any patient receiving one dose of study treatment. For toxicity reporting, all adverse events and laboratory abnormalities will be graded and analyzed using CTCAE version 4 as appropriate.

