1.3 Duration of Study

A treatment cycle is defined as 28 consecutive days.

Patients will receive 6 cycles of induction therapy followed by 6 cycles of maintenance therapy with lower doses of lenalidomide and no dexamethasone for a total of 12 months.

During maintenance, if a patient experiences biochemical progression ($\geq 25\%$ increase and an absolute increase of $\geq 0.5\text{g/dL}$ from their nadir in their serum or urine m-spike or FLC with no CRAB features attributable to MM progression) high-dose dexamethasone may be re-added to the combination at a dose of 40mg oral given on days 1, 8, and 15 of a 28 day cycle after discussion with the overall PI.

For all treatment cycles a $+\text{-} 7$ day window is allowed for Nivolumab. For hold and delay guidelines for lenalidomide and dexamethasone, please refer to Table 17. The treatment plan is designed to be administered on an outpatient basis, however if necessary, may be given as inpatient.

Patients will be followed for up to three years after discontinuation of therapy.

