2.9 Trial Rationale

Based on the activity of lenalidomide and dexamethasone in patients with SMM and based on the data that progression of tumors is based on evasion and suppression of the host immune system, we believe that the combination of a PD-1 inhibitor with lenalidomide will induce high responses and delay development of symptomatic MM in patients with high risk Smoldering MM.

Patients who develop symptomatic disease will receive induction therapy with standard therapeutic options for multiple myeloma including combinations such as those of proteasome inhibitors, immunomodulators and steroids or cyclophosphamide, proteasome inhibitors and dexamethasone.

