5.6 Duration of Follow Up

Participants will be followed for **3 years** after removal from protocol therapy or until progression to active symptomatic MM or need for new therapy, whichever occurs first. Participants removed from protocol therapy for unacceptable adverse event(s) will be followed until resolution or stabilization of the adverse event.

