5.7 Criteria for Taking a Participant Off Study

Participants will be removed from study when any of the following criteria apply:

- Lost to follow-up
- Withdrawal of consent for data submission
- Death
- Progression to active myeloma and subsequent treatment

The reason for taking a participant off study, and the date the participant was removed, must be documented in the case report form (CRF).

CONFIDENTIAL

This document is confidential. Do not disclose or use except as authorized.

A Treatment Ended/Off Study Form will be filled out when a participant is removed from protocol therapy. This form will be provided by the lead site. External sites should submit the form to the Research Project Manager.

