7.4 Expedited Adverse Event Reporting

- Investigators **must** report to the Overall PI any serious adverse event (SAE) that occurs after the initial dose of study treatment, during treatment, or within 30 days of the last dose of treatment on the local institutional SAE form.

For multi-institution studies where a DF/HCC investigator is serving as the Overall Principal Investigator, each participating institution **must** abide by the reporting requirements set by the DF/HCC. This applies to any medical event equivalent to an unexpected grade 2 or 3 with a possible, probable or definite attribution to nivolumab (the study medication), all grade 4 toxicities, and grade 5 (death) regardless of study phase or attribution.

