5- A bone marrow biopsy is required within 6 weeks of registration. A bone marrow aspirate for clinical and research purposes is required pre-treatment and may be performed up to 28 days prior to registration. Both core and aspirate are required any time during the course of the study to confirm CR, and is also required at C7D1

6- Research bone marrow aspirate and biopsy at the same time as clinically indicated bone marrow biopsy and to confirm response.

CONFIDENTIAL

This document is confidential. Do not disclose or use except as authorized.

Local Protocol #: 16-242

Version Date: 23 January 2018

7- Peripheral blood samples for correlative studies may be done at any time pre-treatment, though baseline and C1D1 samples should be considered separate time points.

8-If C7D1 or confirmation of response BM aspirate and core biopsy was performed within 3 weeks of either timepoint, the procedure need not be repeated. At minimum, an aspirate sample is required

9- Disease assessment/response assessment is required each Day 1 starting with C2-If the participant's disease response is not followed primarily via a UPEP (24 hour urine collection) and Urine immunofixation, these tests may be done only at screening, end of treatment, and every 3 months during treatment.

10-A CD of scans at screening and end of treatment is required to be sent to the lead site for central review. Screening scans should be sent with the eligibility packet to the lead site- This requirement includes a full body skeletal survey in addition to spinal MRI OR the patient may have only a low dose PET CT

11- Follow-up should occur every 3 months (+/- 14 days) for up to 3 years after end of treatment.

12- Women of child-bearing potential must abide by revlimid REMS procedures and may require additional pregnancy testing as described in section 3.1.7.

13- Buccal swab may be collected at any time throughout the study but should be collected pre treatment on C1D1

14- Thyroid labs are required at screening, C3D1, C6D1 and every 3 cycles thereafter, at end of treatment, and at any time that it is clinically indicated

15- Alert Overall PI immediately if there is concern for cardiac toxicity (At minimum, the following should be performed: cardiology consult, EKG, echocardiogram, and labs CPK and troponin; refer to section 6.2.7 for more details)

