16- B2M, CRP, and LDH are required at screening, C3D1, C6D1 and every 3 cycles thereafter, at end of treatment, and at any time that it is clinically indicated

17- A disease response assessment will be required at every Day 1 starting with Cycle 2, end of treatment, and every follow up visit (q3 months) until completion, withdrawal, disease progression, subsequent therapy or death

18- All end of treatment assessments will be performed within 14 days from the date that the decision to end treatment was made by the study team

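### A Kaplan-Meier overall survival estimate is planned, but no vital-status follow-up is provided for after progression, so survival is expected to be overstated

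*Combined protocol and SAP*

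**What the plan says.** Section 13.1.2 lists OS among the time-to-event analyses: "overall survival (time from protocol therapy initiation to death or date last known alive), the Kaplan-Meier method will be used". It is not among the secondary objectives in section 1.5.

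The follow-up rules are spread over several places:

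- Section 5.6 follows participants for 3 years after they leave protocol therapy, "or until progression to active symptomatic MM or need for new therapy, whichever occurs first".
- Section 5.7 lists, among the reasons for removal from study, "Progression to active myeloma and subsequent treatment".
- Section 2.9 makes treatment after progression the norm: "Patients who develop symptomatic disease will receive induction therapy with standard therapeutic options for multiple myeloma".
- Section 10 (study calendar), footnote 17, requires response assessment at "every follow up visit (q3 months) until completion, withdrawal, disease progression, subsequent therapy or death". The calendar has no row for survival status.
- Section 1.3 states: "Patients will be followed for up to three years after discontinuation of therapy". Calendar footnote 11 states: "Follow-up should occur every 3 months (+/- 14 days) for up to 3 years after end of treatment". Neither repeats the stop at progression.
- Section 7.4 requires reports of serious adverse events up to "within 30 days of the last dose of treatment on the local institutional SAE form".

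**The concern.** Kaplan-Meier is valid for OS only if patients censored at a given time have the same later risk of death as those still followed. Here the event that ends follow-up is progression to active disease, which treatment aims to delay and which is expected to raise the risk of death. Patients would leave the risk set because their prognosis had changed, and their later deaths would mostly go unrecorded. The plan names an endpoint for which its own follow-up rules do not collect the data, and it gives no rule for handling such censoring.

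At stake is one descriptive secondary estimate. Section 2.6 cites 3-year survival of 94% versus 80% from the earlier randomized trial, so a survival figure from this trial that is several points too high could mislead. No comparison with that trial's survival is planned.

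**Working it through.** **1. The plan's own figures.** No OS figure is stated. The primary design in section 13.1 reproduces by exact binomial: 24 or more of 39 has probability 0.0998 at a true rate of 50% and 0.906 at 70%, matching the stated 0.10 and >0.9. That rule does not use OS.

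**2. The follow-up rules side by side.** Section 5.6 stops at progression to active disease or need for new therapy. Section 5.7 needs progression and subsequent treatment, which section 2.9 makes the usual sequel. Sections 1.3 and 10 (footnote 11) give a 3-year period but do not provide for survival contact after progression. Adverse event reporting reaches only 30 days past the last dose. Nothing fills the gap.

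**3. Model.** Three states (progression-free, progressed, dead) with constant yearly hazards: λ for progression, m0 for death before progression and m1 for death after it.

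- True OS(t) = exp(−(λ+m0)t) + λ[exp(−m1·t) − exp(−(λ+m0)t)] / (λ+m0−m1).
- Kaplan-Meier with every progressor censored at progression tends to exp(−m0·t).
- λ = −ln(2-year progression-free rate)/2. This gives 0.178 at 70% and 0.347 at 50%, the target and null rates in section 13.1. It treats progression in that section as the event that ends follow-up, in line with section 11.1.

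**4. Inputs the documents do not give.** m0 is assumed to be 0.005 to 0.03 per year. m1 is set so that the observation arm cited in section 2.6 (median time to progression 21 months, hence λ = ln 2/1.75 = 0.396) has 80% survival at 3 years. The resulting m1 falls from 0.188 to 0.143 as m0 rises.

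**5. One case in full.** Take m0 = 0.02, m1 = 0.16 and 70% progression-free.

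- λ+m0 = 0.1983; exp(−0.595) = 0.5516; exp(−0.48) = 0.6188.
- True 3-year OS = 0.5516 + 0.1783 × (0.6188 − 0.5516)/0.0383 = 0.864.
- Kaplan-Meier censored at progression: exp(−0.06) = 0.942.
- Excess: 7.8 points.

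**6. Results at 3 years.**

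| m0 | m1 | Censored Kaplan-Meier | True OS, 70% progression-free | Excess (points) | True OS, 50% progression-free | Excess (points) |
|---|---|---|---|---|---|---|
| 0.005 | 0.188 | 0.985 | 0.884 | 10.1 | 0.816 | 16.9 |
| 0.01 | 0.178 | 0.970 | 0.877 | 9.3 | 0.815 | 15.6 |
| 0.02 | 0.160 | 0.942 | 0.864 | 7.8 | 0.812 | 12.9 |
| 0.03 | 0.143 | 0.914 | 0.852 | 6.2 | 0.810 | 10.4 |

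With m1 = 0.05 and m0 of 0.01 to 0.02, the excess is 1.9 to 2.5 points at 70% and 3.1 to 4.2 points at 50%. With m1 = m0 it is zero.

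**7. How many patients.** The number who progress by time t is 41 × λ/(λ+m0) × [1 − exp(−(λ+m0)t)]. With m0 of 0.01 to 0.02, about 12 of the planned 41 would progress by 2 years and 17 by 3 years at a 70% progression-free rate. At 50% the figures are about 20 and 26.

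**The case against.** The strongest reply is that the documents conflict rather than exclude later deaths outright. Section 5.7 needs both progression and new treatment, so a death between the two occurs on study. Sections 1.3 and 10 give up to three years without a progression stop. The OS definition ends at the date last known alive, whereas the PFS definition in the same sentence ends at the date last known progression-free, so any later vital-status information would be used. Biochemical progression in maintenance does not by itself end treatment or follow-up (sections 1.3, 5.5 and 5.7), so deaths after it stay visible.

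All of this stands. A reader might infer that no death after progression is ever seen, or that every progressor is censored at progression. The documents do not support that. They support the narrower statement that survival follow-up after progression is not provided for. Chance reports of some later deaths would make ascertainment uneven and would not make the censoring uninformative.

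It is also fair that the size is assumed and that OS carries no hypothesis or decision rule. A reader might take a much higher post-progression death rate and obtain a larger bias. At 0.30 per year, with m0 = 0.01 and 70% progression-free, 3-year OS would be 0.97 against 0.83. That rate would put the cited observation arm at about 71% 3-year survival, against the reported 80%. Figures at 4 years should not be used either: section 13.2 expects 1.5 years of accrual and ends the study at most 2 years after the last start, so the longest follow-up at the final analysis is about 3.5 years.

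**Conclusion.** The point holds as a gap between a planned endpoint and the follow-up meant to supply it. Followed as written, the plan would miss most deaths after progression and give an OS curve that is expected to be too high. The direction depends on the death hazard being higher after progression than before.

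At 3 years the excess is about 6 to 10 points with 70% progression-free at 2 years, and about 10 to 17 points with 50%, when the post-progression hazard is matched to the cited observation arm. It is about 2 to 4 points at 0.05 per year and zero if progression adds no risk. These figures assume constant hazards, an assumed m0 and censoring of all progressors at progression, so any later deaths that are captured would change them. The patient counts assume 41 enrolled, and the September 2017 hold closed accrual. A smaller sample would not remove the bias.

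Two further inferences should be avoided. The curve does not estimate the probability of death without progression. With m0 = 0.01 and 70% progression-free, that probability is (0.01/0.1883) × (1 − exp(−0.565)) = 2.3% at 3 years, while one minus Kaplan-Meier is 1 − exp(−0.03) = 3.0%. The curve reflects the pre-progression death hazard alone. Nor is the trial's conclusion affected, because OS is outside the objectives and the primary rule of 24 of 39, with its error rates, does not depend on it. The change should be made, but it is not critical to the primary result.

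**What to change.** Choose one of two changes:

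1. Delete OS from section 13.1.2 and report deaths without progression descriptively. This costs nothing.
2. Keep OS and amend sections 5.6 and 5.7 so that vital status is collected, from records or by phone, for every treated patient to a common cut-off date regardless of progression or new therapy. The cost is small: an amendment, possibly consent for continued contact, and no added visit or procedure. The consent pages were not available to check.

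In either case, reconcile sections 1.3, 5.6 and 5.7 and calendar footnote 11 so that they state one end of follow-up. Without the second change, do not report a Kaplan-Meier OS estimate.

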2.9.2 Stem Cell Mobilization and Collection

Patients who are eligible for stem cell collection and who intend to go on to transplant will have the option to collect stem cells during the course of therapy on this trial at the time of best response (PR, VGPR, or CR or at investigator's discretion) or after 6 cycles of induction therapy, however, collection may be done at any time during the study after discussion with the Overall PI. Institutional guidelines should be followed in regards to stem cell mobilization and collection. Patients should be mobilized as soon as possible after stopping study treatment. Patients may delay resuming treatment for up to 3 weeks after collection is complete.

Plerixafor should be utilized as a mobilization agent primarily; however cyclophosphamide or other agents may be used at the investigator's discretion. Based on data using combination therapies for induction, there have been no major concerns regarding stem cell collections after treatment with these agents.

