5. TREATMENT PLAN

5.1 Treatment Regimen

Treatment will consist of 6 cycles of induction therapy followed by maintenance therapy for a total of 12 months. A treatment cycle is defined as 28 consecutive days.

For treatment cycles 1 through 12, a +/- 7 day window for nivolumab dosing is allowed. For further guidance on lenalidomide and dexamethasone holds and delays, please see Table 17. No investigational or commercial agents or therapies other than those described below may be administered with the intent to treat the participant's malignancy.

** As of September 2017, the trial has been put on partial clinical hold by the Food and Drug Administration: all patients are to discontinue nivolumab indefinitely, and no additional patients will be accrued to the trial. Participants may elect to remain on lenalidomide/dexamethasone or lenalidomide therapy alone for disease control after discussion with the overall PI.

Induction Cycles

Table 7: Nivolumab and Lenalidomide and Dexamethasone Combination (Cycles 1-6)

Agent	Pre-medications/ Precautions	Dose	Route	Schedule	Cycle Length
Nivolumab	None	240 mg	Intravenous	Days 1,15	28 days
Lenalidomide	None	25 mg	Oral	Days 1-21 of each cycle	
Dexamethasone	Take with food; Recommended to be taken in the morning	40 mg	Oral	Days 1, 8, 15	

Maintenance Cycles**

Table 8: Nivolumab and Lenalidomide Combination (Cycles 7-12)

Agent	Pre-medications/ Precautions	Dose	Route	Schedule	Cycle Length
Nivolumab	None	240 mg	Intravenous	Days 1, 15	28 days
Lenalidomide	None	15 mg*	Oral	Days 1-21 of	

CONFIDENTIAL

This document is confidential. Do not disclose or use except as authorized.

				each cycle	
--	--	--	--	------------	--

* If patient was dose reduced during the induction phase for lenalidomide below 15mg, then maintenance phase starts at that dose reduction and not at the higher 15 mg dose.

** During maintenance, if a patient experiences biochemical progression ($\geq 25\%$ increase and an absolute increase of $\geq 0.5\text{g/dL}$ from their nadir in their serum or urine m-spike or FLC with no CRAB features attributable to MM progression) high-dose dexamethasone may be re-added to the combination at a dose of 40mg oral given on days 1, 8, and 15 of a 28 day cycle after discussion with the overall PI.

The participant will be requested to maintain a medication diary. The medication diary should be returned to clinic staff at the end of each cycle.

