5.3 General Concomitant Medication and Supportive Care Guidelines

5.3.1 Medications and supportive care

- Patients who experience worsening neuropathy from baseline should be observed for recovery, have dose reductions/delays as indicated in the protocol, and any supportive therapy or intervention may be initiated as appropriate at the discretion of the investigator.
- Supportive measures consistent with optimal patient care may be given throughout the study.
- Stem cell collection may be performed at the time of best response (PR, VGPR or CR or at the investigator's discretion) or after 6 cycles of therapy for those who are transplant eligible, and/or who plan to pursue transplant in the future. The standard mobilization procedures of the treating institution should be followed. Plerixafor should be the preferred mobilization agent, though cyclophosphamide or other agent may be used at the investigator's discretion. A delay of no more than 3 weeks is allowed between the end of collection and re-initiation of therapy especially if chemotherapy such as high dose cyclophosphamide was used for stem cell mobilization. Mobilization should occur as soon as possible after study treatment is stopped.
- Use of white cell growth factors (Filgrastim or acceptable equivalent) is allowed for management of treatment-induced neutropenia at physician discretion. Filgrastim or equivalent should be given according to local institutional guidelines or per the package insert. Pegfilgrastim is not to be used in place of filgrastim.
- Patients may be transfused with red cells and platelets as clinically indicated and according to institutional guidelines.
- Patients may receive bisphosphonates per recommendations of myeloma therapy, or may follow local standard of care. A note should be placed about patients who are not receiving bisphosphonates, such as osteonecrosis of the jaw.
- If nausea and/or vomiting is/are noted at any point in time, premedication with prochlorperazine or other antiemetics may be used before future doses. Antiemetics, including 5-HT3 serotonin receptor antagonists, may be used as needed at the discretion of the investigator.

CONFIDENTIAL

This document is confidential. Do not disclose or use except as authorized.

- If nausea persists in spite of the use of standard antiemetics, additional symptom management should be initiated per institutional standard.

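### Minor: the CTX-free 2-year PFS rule misses its stated type I error at n=32 (taking the rates as the subset's own), and the subset is chosen by a post-baseline event

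*Combined protocol and SAP*

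**What the plan says.** Section 13.1.2 expects about 20% of patients to receive cyclophosphamide (CTX) for mobilisation, says this may influence PFS, and plans that "in a secondary analysis the 2 year PFS rate will be evaluated among those patients who did not receive CTX". PFS in that section runs from initiation of protocol therapy.

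For CTX use of 5-20% among 39 eligible patients, the rule is that "the treatment will be considered promising if the observed response rate is at least 62" per cent. The claimed performance is that "there is at least 80% probability of concluding the treatment is effective, when the true rate is 70% and less than 10% if true"; the second of these figures refers to a true rate of 50%.

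On mobilisation, section 2.9.2 gives transplant-eligible patients the "option to collect stem cells during the course of therapy on this trial at the time of best response" or after six induction cycles, and adds that "collection may be done at any time during the study after discussion with the Overall PI". Section 5.3.1 says: "Plerixafor should be the preferred mobilization agent, though cyclophosphamide or other agent may be used at the" investigator's discretion.

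Section 13.1 sets the primary rule at 24 or more of 39 (an observed rate printed as 62%) and says that its error probabilities are exact binomial.

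**The concern.** There are two separate questions.

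First, 5-20% of 39 is 2 to 7 whole patients, which leaves 32 to 37 without CTX. At these sizes type I error and power move in visible steps from one n to the next. A percentage cut-off with one pair of error rates for the whole range therefore has to be checked size by size.

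Second, nobody's membership of the subset is known when the PFS clock starts. A patient leaves it by receiving CTX later, at a time tied to best response or to completing six cycles. The plan gives no landmark, censoring or time-dependent handling for this. A verdict of promising is nevertheless attached to the subset, and it could differ from the primary result because of who was removed, not because of any effect of CTX.

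The rule also speaks of a response rate where the endpoint is the 2-year PFS rate. Objective response rate is a different endpoint in the same section.

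**Working it through.** **Inputs.** From section 13.1: null rate 0.50, alternative 0.70, rule 24/39, exact binomial method. From section 13.1.2: cut-off 62%, CTX use 5-20% of 39, claimed power at least 0.80 and type I error below 0.10. Using the exact method for the secondary rule is an inference, because the sentence naming it sits with the primary design.

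**Formula.** With X ~ Binomial(n, p) and cut-off r, type I error = P(X ≥ r | p = 0.50) and power = P(X ≥ r | p = 0.70).

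**Primary rule reproduced.** n = 39, r = 24: type I error 0.0998, power 0.906. This agrees with section 13.1.

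**Secondary rule.** r is the smallest integer with r/n ≥ 0.62, and the rates are taken as the subset's own.

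| CTX patients (of 39) | n | r | Type I error | Power | Both claims met |
|---|---|---|---|---|---|
| 7 (17.9%) | 32 | 20 | 0.108 | 0.867 | no |
| 6 (15.4%) | 33 | 21 | 0.081 | 0.839 | yes |
| 5 (12.8%) | 34 | 22 | 0.061 | 0.807 | yes |
| 4 (10.3%) | 35 | 22 | 0.088 | 0.865 | yes |
| 3 (7.7%) | 36 | 23 | 0.066 | 0.837 | yes |
| 2 (5.1%) | 37 | 23 | 0.094 | 0.887 | yes |

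Eight CTX patients would be 20.5%, just outside the range; n = 31 with r = 20 gives 0.075 and 0.808, which meets both.

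**Other cut-offs at n = 32.** r = 19: 0.188 and 0.931. r = 21: 0.055 and 0.772. r = 22: 0.025 and 0.644. As r rises both quantities fall, so no integer cut-off meets both claims.

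**Reading of 62%.** Section 13.1 prints 24/39 = 61.5% as 62%. If the secondary cut-off is also 24/39, then at n = 34 it becomes 34 × 24/39 = 20.9, so r = 21, with type I error 0.115 and power 0.890. That size then fails too. The other sizes from 32 to 37 keep the same r.

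**Selection, illustration only.** The documents give no CTX dates. Assume exponential times to event, no effect of CTX, and recipients who are event-free at mobilisation at month m but otherwise typical. With cohort 2-year rate p and CTX share f = (39 − n)/39:
- rate in recipients: q = p / p^(m/24)
- rate in the rest: (p − q·f)/(1 − f)

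Smallest shift at p = 0.70 (n = 37, m = 3): q = 0.732, f = 0.0513, subset rate 0.698, or −0.2 points. Largest (n = 32, m = 12): q = 0.837, f = 0.1795, subset rate (0.700 − 0.150)/0.8205 = 0.670, or −3.0 points. The sampling SD at n = 32 is √(0.7 × 0.3/32) = 0.081.

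**Alternative estimator, simulated.** 40,000 cohorts of 39, seven mobilised with CTX at 6 months, true 2-year rate 0.70, no CTX effect:
- random event-free recipients: full cohort 0.700 (SD 0.073), exclusion 0.686 (0.082), Kaplan-Meier censored at CTX 0.700 (0.080)
- only responders mobilised, 79% responders assumed (the post-induction figure quoted in section 2.6), non-responder hazard 2, 3 or 4 times higher: exclusion about 0.679, 0.674, 0.671; Kaplan-Meier about 0.694, 0.688, 0.686

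Censoring removes all of the selection in the first case and part of it in the second.

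**The case against.** The strongest reply is that the miss is one point on a lattice: 0.8 percentage points of type I error at one of six sizes, in a secondary analysis. The rounded ends of the range (n = 31 and n = 37) do reproduce the claim. If 5-20% is read as a probability of receiving CTX, so that the subset size is random, averaging gives type I error 0.076 to 0.093 and power 0.837 to 0.860, and both claims hold. A normal approximation at n = 32 would also pass (0.087 and 0.838). All of this is correct. But the section mentions no averaging, and exact binomial is the only method the plan names. A rule applied to the subset actually obtained should have its error rates stated for that subset.

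A reader might go further and infer that the two rates can never both hold at n = 32. That needs the rates to be the subset's own, and the section says only the true rate. If 50% and 70% are cohort rates and the 6-month selection model above applies, 20/32 gives 0.070 and 0.825, and both hold. The numerical and selection points therefore rest on different assumptions and should not be added together.

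A reader might also infer a known direction of bias. Downward is what the illustration gives, but it assumes no CTX effect and typical, event-free recipients. Upward might be inferred because "During maintenance, if a patient experiences biochemical progression", "high-dose dexamethasone may be re-added to the combination", so such a patient could still be on therapy and be mobilised later. That allowance covers maintenance only. It also matters only if biochemical progression counts as a PFS event, as the progression table in section 11.2.2.1 suggests, whereas section 11.1 names symptomatic myeloma as the final endpoint. The documents support neither direction firmly.

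Finally, the primary analysis already keeps all patients who received a dose, so an unselected estimate exists. That stands, and it limits the weight of the point.

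**Conclusion.** The point holds and is minor. Under exact binomial tails, with 50% and 70% taken as the subset's own rates, the claimed pair of error rates is met at n = 33 to 37 and missed at n = 32. It is also missed at n = 34 if 62% means 24/39. The excess in type I error is under 1 percentage point at n = 32 and about 1.5 at n = 34.

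Selection on CTX receipt means that the subset's 2-year PFS rate need not estimate the cohort's rate even if CTX does nothing. The illustrated shift of 0.2 to 3.0 points at a 70% cohort rate is well below the sampling SD of about 8 points and rests on assumed dates and prognosis.

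Nothing here touches the primary decision at 24/39. Section 1.1 records that accrual has stopped and the documents do not give the number enrolled, so whether a subset of 32 to 37 will arise is unknown.

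**What to change.** In section 13.1.2:
- State the integer cut-off with its exact type I error and power for the n actually analysed or, failing that, for each n from 32 to 37.
- Say that these refer to the subset's own true rate, and whether the cut-off is 62% or 24/39.
- Correct n = 32: either type I error 0.108 at 20/32 or power 0.772 at 21/32.
- Replace response rate with 2-year PFS rate.
- Add a sensitivity analysis that keeps all treated patients and estimates 2-year PFS by Kaplan-Meier, which the section already names for PFS. Censor at the date of CTX mobilisation, count earlier PFS events, and give a 90% CI. Note that this censoring may be informative, because mobilisation is tied to response.

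The cost is a few sentences, plus the CTX date on the case report form if it is not already collected. In the simulation the censored estimate is slightly less precise than the full cohort (SD 0.080 against 0.073), and if only responders are mobilised a downward bias of about 0.6 to 1.4 points remains.
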